9.4.5 Post Treatment (Part C)

Visit Day 7 (40 – 48 Hours Post-Dose 10) Follow-up:

Note: Visit Day 7 may occur on Study Days 7 or 8 depending on when the subject received his or her first dose of IMP.

- Physical examination
- Evaluation of hydration status
- Body weight/length/head circumference
- Vital signs (body temperature, systolic and diastolic BP, HR, RR)
- 12-Lead ECG
- Record RSV-related signs and symptoms, and severity (if indicated), including: temperature, cough, coryza, grunting with expiration, nasal flaring, retractions, and wheezing
- ReSVinet scale for clinicians ([Appendix 17.6](#))
- Adapted ReSVinet Scale for Parental use ([Appendix 17.2](#))
- Safety laboratory tests (clinical chemistry and haematology)
- Urinalysis
- PK blood sample according to sampling schedule in [Table 5](#)
- Nasopharyngeal swab
- Concomitant medication review
- Adverse event review

Visit Day 14 Follow-up:

- Vital signs
- Body weight/length/head circumference
- Record RSV-related signs and symptoms, and severity (if indicated), including: temperature, cough, coryza, grunting with expiration, nasal flaring, retractions, and wheezing
- ReSVinet scale for clinicians ([Appendix 17.6](#))
- Adapted ReSVinet scale for parental use ([Appendix 17.2](#))
- Nasopharyngeal swab
- Concomitant medication review
- Adverse event review

Visit Day 34 Follow-up:

- Vital signs
- Body weight/length/head circumference
- Record RSV-related signs and symptoms, and severity (if indicated), including: temperature, cough, coryza, grunting with expiration, nasal flaring, retractions, and wheezing

- ReSVinet scale for clinicians ([Appendix 17.6](#))
- Adapted ReSVinet scale for parental use ([Appendix 17.2](#))
- Nasopharyngeal swab
- Concomitant medication review
- Adverse event review

Early Withdrawal (or Discontinuation) Visit

Parents/legal guardians who withdraw their child from the study will be encouraged to allow their child to complete the same final evaluations as subjects completing the study according to this protocol (ie, at the relevant post-treatment visit), particularly safety evaluations.

9.5 Duration of Treatment

Part A:

Subjects will participate for up to 8 days. A single oral dose of RV521 will be administered in Part A, and the visit schedule will include:

- Screening Visit (-24 hours)
- Dosing Visit 1 (-2 pre-dose to 18-24 hours post-dose)
- Post-dosing Visit 2 (48 hours post-dose)
- Telephone Follow-up (Day 7)

Part B:

Subjects will participate for up to 13 days. The proposed dosing regimen for Part B is RV521 or placebo administered BID, 12 hours apart, for a period of 5 consecutive days (for a total of 10 doses), and the visit schedule will include:

- Screening Visit (-24 hours)
- Dosing Visit 1 (-2 to 18-24 hours post-dose)
- Dosing Visit 2
- Dosing Visit 3
- Dosing Visit 4
- Dosing Visit 5
- Follow-Up Visit Day 7 (+40-48 Hours Post-Dose 10)
- Telephone Follow-Up (Day 12)

Note: The actual day of each Dosing Visit will be dependent upon the time that the subject receives their first dose of IMP on Visit 1. Follow-Up Visit Day 7 may therefore fall on Study Days 7 or Day 8 depending upon the time the subject received his or her first dose of IMP on Dosing Visit 1.

Part C:

Subjects will participate for up to 35 days, and the visit schedule will include: Screening (24 hours to first dose), Dosing Visits 1 to 5 (5 days), and follow-up 40-48h Post-Dose 10 (Study

Days 7 or 8) and at Study Days 14 and 34. Inpatient duration will be determined clinically by the PI or other health care provider and by ability to complete study procedures and assessments on an outpatient basis ([Section 9.4](#)). Follow-up days are expected to be on an outpatient basis.

10 PHARMACOKINETICS, EFFICACY AND SAFETY VARIABLES

The planned Schedule of Assessments is in [Section 8.1](#).

The intended volume of blood to be withdrawn for each of the assessments is based on the minimal, reasonably required volume for each of the respective analyses and is below those allowed per the WHO and European and United States guidance.

In order to limit the volume of blood to be collected, the normal protocol-driven tests will only be performed within the indicated time frame as part of the standard of care.

For safety tests (haematology and chemistry), a total of 4.2 mL of blood will be drawn, per protocol (all study parts).

For PK analysis, 0.2 mL of whole blood is required at each sampling time point. Thus, for a maximum of 6 PK samples (Part B), 1.2 mL of whole blood will be required.

The maximum amount of blood that will be taken for the study will be 5.4 mL.

Collection schedules may switch between the cannulation and heel prick methods dependent upon the presence and availability of a patent IV cannula as well as the sample purpose (PK versus safety evaluations).

Complete instructions for collection, processing, handling, and shipment of all safety laboratory tests, PK, and nasopharyngeal swab samples will be provided in the Laboratory Manual.

10.1 Pharmacokinetics, Efficacy, and Safety Assessments

10.1.1 Pharmacokinetic Assessments

Blood samples for measurement of serum concentrations of RV521 will be drawn at time points specified in the Schedule of Assessments in [Section 8.1](#). The actual date and time (24-hour clock time) of each sampling will be recorded in the subject's source document at the site. The sampling window for each time point is identified in [Table 1](#), [Table 2](#), and [Table 5](#). Plasma samples for determination of RV521 concentrations will be analysed by a central laboratory using a validated assay method. Full details of the analytical methods used will be described in a separate bioanalytical report. Deviations from planned sampling windows will be assessed before database lock for the impact on PK analyses and may be excluded from time point summaries of PK concentrations. Actual time will be used for derivation of PK parameters.

If a subject experiences an AE Grade 3 or higher or meets SAE criteria, a blood sample for the measurement of serum concentrations of RV521 should be collected (if less than 24 hours have elapsed since the last dose of IMP and more than 24 hours since the last PK sample), if possible. The sample will be recorded as an unscheduled time point and may be also used in PK parameters derivation using actual time.

10.1.2 Efficacy Assessments

10.1.2.1 Viral Load Assessments

A single nasopharyngeal swab sample for the measurement of RSV viral load will be taken at each time point identified in the Schedule of Assessments for Part A (Table 1), Part B (Table 2), and Part C (Table 3a inpatients and Table 3b outpatients) in Section 8.1. The actual date and time (24-hour clock time) of each sampling will be recorded in the subject's source document at the site. Deviations from planned sampling windows will be assessed before database lock for the impact on PD analyses. Actual time will be used for derivation of PD parameters.

Cell-based infectivity assay and RT-qPCR assay will be used to quantify RSV viral load in nasopharyngeal swab samples. CCI [REDACTED]

[REDACTED]

[REDACTED]

10.1.2.2 Clinical Response Assessments

Clinical response will be measured by evaluation of the RSV signs and symptoms list (all Parts), RSV Clinical Scoring System (Parts A and B), the ReSVinet Score for Clinicians (Part C), and the adapted version of ReSVinet scale for parental use (Parts B and C). In addition, CCI [REDACTED] and time to normalisation of respiratory rate will be analysed in Part C. Details of how the clinical efficacy endpoints will be analysed, and by which scales, is briefly described in Section 11.1.5 and will be outlined in the Statistical Analysis Plan.

10.1.3 Safety Assessments

Safety assessments will consist of AEs, haematology, clinical chemistry, urinalysis, vital signs, physical examination, and ECGs.

10.1.3.1 Adverse Events

Adverse Event Definition

An AE is defined as any untoward medical occurrence in a clinical study subject administered a medicinal product which does not necessarily have a causal relationship with this treatment. An AE can therefore be any unfavourable and unintended sign (including an abnormal laboratory finding), symptom, or disease temporally associated with the use of a medicinal (investigational) product, whether or not it is related to the medicinal (investigational) product. This includes an exacerbation of pre-existing conditions or events, intercurrent illnesses, drug interaction or the significant worsening of the indication under investigation that is not recorded elsewhere in the

CRF under specific efficacy assessments. Anticipated fluctuations of pre-existing conditions, including the disease under study that does not represent a clinically significant exacerbation or worsening need not be considered AEs.

It is the responsibility of the Investigator to document all AEs that occur during the study from the time the ICF is signed. AEs and SAEs should be followed until resolution or until the event is stable. An AE should be reported on the appropriate page of the CRF.

Each separate AE episode must be recorded. For example, if an AE resolves completely or resolves to baseline and then recurs or worsens again, this must be recorded as a separate AE. For AEs to be considered intermittent, the events must be of similar nature and severity.

Adverse Reaction Definition

An adverse reaction is any untoward and unintended response that is related to the administration of the IMP at any dose.

Onset Date, End Date

If an AE starts during the study but did not end before the final closing (follow-up) visit, the Investigator must make a reasonable effort to establish the outcome and the end date of the AE. If this is not possible (eg, because the AE is still ongoing) or the subject is lost to follow-up, there will be no end date for the AE.

For all AEs that resolve, resolve with sequelae, or have a fatal outcome, an end date must be provided.

If an AE stops and restarts later, all occurrences have to be recorded separately.

Assessment of Severity

Severity of AEs will be assessed by the Investigator using NCI CTCAE v5.0, 27 November 2017 ([CTCAE v5.0](#)). Grades of the NCI CTCAE refer to the severity of the AE as follows:

- Grade 1 Mild; asymptomatic or mild symptoms; clinical or diagnostic observations only; intervention not indicated.
- Grade 2 Moderate; minimal, local or non-invasive intervention indicated; limiting age-appropriate instrumental Activities of Daily Living (ADL).
- Grade 3 Severe or medically significant but not immediately life-threatening; hospitalisation or prolongation of hospitalisation indicated; disabling; limiting self-care ADL.
- Grade 4 Life-threatening consequences; urgent intervention indicated.
- Grade 5 Death related to AE.

If there is a change in severity of an AE, every episode of the AE will be captured separately and all required information for every episode will be provided separately.

Assessment of Causality

Every effort will be made by the Investigator to assess the relationship of the AE, if any, to the IMP. Causality should be assessed using the categories presented in the following table:

Unrelated:	Clinical event with an incompatible time relationship to IMP administration, and that could be explained by underlying disease or other drugs or chemicals or is incontrovertibly not related to the IMP.
Unlikely:	Clinical event whose time relationship to IMP makes a causal connection improbable, but that could plausibly be explained by underlying disease or other drugs or chemicals.
Possibly:	Clinical event with a reasonable time relationship to IMP, but that could also be explained by concurrent disease or other drugs or chemicals.
Probably:	Clinical event with a reasonable time relationship to IMP, and is unlikely to be attributed to concurrent disease or other drugs or chemicals.
Definitely:	Clinical event with plausible time relationship to IMP, and that cannot be explained by concurrent disease or other drugs or chemicals.

Action Taken with IMP

The Investigator will describe the action taken in the appropriate section of the CRF, as follows:

- None (no action taken)
- Unknown
- IMP temporarily interrupted – only for Part B and Part C (date, time and reason to be provided)
- IMP permanently discontinued (date and reason to be provided)
- Other (to be specified)

Outcome of Adverse Event

The final outcome of the AE will be documented in the appropriate section of the eCRF, as follows:

- Recovered
- Recovered with Sequelae
- Ongoing
- Unknown
- Death

Follow-up of Adverse Events

All Investigators should follow up subjects with AEs or SAEs until the event is resolved or until, in the opinion of the Investigator, the event is stabilised or determined to be chronic. Details of AE or SAE resolution must be documented in the CRF.

Subjects should be followed up to the last follow-up visit, (ie, Day 7 after receiving the last dose of IMP in Part A, Day 12 in Part B, and Day 34 in Part C) and any AEs that occur during this time should be reported according to the procedures outlined above.

For all SAEs, where important or relevant information is missing, active follow-up should be undertaken.

A follow-up report must be completed when an SAE resolves, is unlikely to change, or when additional information becomes available. In case the SAE is a suspected unexpected serious adverse reaction (SUSAR), follow-up information must be provided within the timelines as requested by Syneos Health Safety & Pharmacovigilance.

If new or amended information on a reported SAE becomes available, the Investigator can report this on a new SAE form using the completion guidelines. If using the original form to notify further information, all new or amended information need to be initialled and dated in order all changes are clearly identified.

Documentation and Reporting of Adverse Events

An AE should be reported and documented in accordance with the procedures outlined below. All AEs occurring during the study must be documented on the relevant CRF pages. The following data should be documented for each AE:

- Diagnosis, if not available, symptoms
- Classification of ‘serious’ or ‘not serious’
- Severity
- Date and time of first occurrence and date and time of resolution (if applicable)
- Action taken with the IMP
- Causal relationship
- Outcome of event (unknown, recovered, ongoing, recovered with sequelae, death [with date, time, and cause reported])

10.1.3.2 Serious Adverse Events

Serious Adverse Event Definition

An SAE is any untoward medical occurrence or effect that, at any dose,

- Results in death
- Is life-threatening (an AE is life-threatening if the subject was at immediate risk of death from the event as it occurred, ie, it does not include a reaction that might have caused death if it had occurred in a more serious form)
- Requires or prolongs inpatient hospitalisation. (Complications occurring during hospitalisation are AEs and are SAEs if they cause prolongation of the current hospitalisation. Hospitalisation / Prolonged hospitalisation for elective treatment of a pre-existing non-worsening condition is not, however, considered an AE. The details of such hospitalisations must be recorded on the medical history or physical examination page of the CRF)
- Results in persistent or significant disability/incapacity. (An AE is incapacitating or disabling if it results in a substantial and/or permanent disruption of the subject’s ability to carry out normal life functions)

In addition, medical and scientific judgement is required to decide if prompt notification is required in situations other than those defined for SAEs above. This may include any event that the Investigator regards as serious that did not strictly meet the criteria above but may have jeopardised the subject or required intervention to prevent 1 of the outcomes listed above, or that would suggest any significant hazard, contraindication, side effect, or precaution that may be associated with the use of the investigational product.

Reporting of Serious Adverse Events

Any SAE must be reported by the Investigator if it occurs during the clinical study from signature of Informed Consent through to the last scheduled Study Visit, whether or not the SAE is considered to be related to the IMP. If an AE becomes an SAE, the start date of the SAE is the date that the AE fulfils any seriousness criterion. The stop date of an SAE is the date that the event resolves or no longer fulfills the seriousness criterion.

An SAE report consists of the SAE form. SAE reports should be sent **within 24 hours** by e-mail to the Syneos Health Safety and Pharmacovigilance department:

[contact] [REDACTED]

The Investigator will be requested to supply as much detailed information regarding the event that is available at the time of the initial report (examinations carried out, laboratory results etc.).

The Investigator is also required to submit follow-up reports as soon as possible, and within 24 hours of becoming aware of any additional information such as diagnosis, outcome, causality assessment, results of specific investigations and any new significant information that has not been previously reported.

The Investigator should not wait to receive additional information to document fully the event before notification of an SAE, although additional information may be requested by the Syneos Health pharmacovigilance department. Where applicable, information from relevant laboratory results, hospital case records, and autopsy reports should be obtained.

Instances of death, or an event that is of such clinical concern as to influence the overall assessment of safety, if brought to the attention of the Investigator at any time after cessation of IMP administration and linked by the Investigator to this study, should be reported to the study monitor.

Syneos Health, on behalf of the Sponsor will promptly notify all relevant Investigators and the regulatory authorities of findings that could adversely affect the safety of subjects, impact on the conduct of the study or alter the independent ethics committee (IEC)/institutional review board (IRB) approval/favourable opinion of the study. In addition, Syneos Health, on behalf of the Sponsor, will expedite the reporting to all concerned Investigators, to the IECs/IRBs, where required, and to the regulatory authorities of all adverse reactions that are both serious and unexpected according to local safety reporting requirements.

10.1.3.3 Unexpected Adverse Reactions

Unexpected Adverse Reaction Definition

An unexpected adverse reaction is any untoward and unintended response that is related to the administration of the IMP at any dose that is not consistent with the applicable RSI (eg, [IB] for an unauthorised IMP or summary of product characteristics for an authorised product). The expectedness of an adverse reaction is determined by the Sponsor in the RSI.

For this protocol, the RSI for the assessment of expectedness is included in the most recent fully approved version of the IB for RV521.

All SUSARs will be the subject of expedited reporting. Syneos Health shall ensure that all relevant information about a SUSAR that is fatal or life-threatening is reported to the relevant competent authorities and IEC/IRB, within 7 days after knowledge by the Sponsor of such a case and that relevant follow-up information is communicated within an additional 8 days and/or according to local safety reporting requirements. All other SUSARs will be reported to the

relevant competent authorities and IEC/IRB within 15 days after knowledge by the Sponsor of such a case and/or according to local safety reporting requirements. All Investigators should follow up SUSARs until the event is resolved or until, in the opinion of the Investigator, the event is stabilised or determined to be chronic. Post-study SUSARs that occur after the subject has completed the clinical study must be reported by the Investigator to the Sponsor.

Warnings and Precautions

Please refer to the IB for RV521 (summary of data, reference safety information, and guidance for the Investigator).

10.1.3.4 Clinical Laboratory Assessments

The following laboratory safety tests will be performed according to the relevant Schedule of Assessments for Part A (Table 1), Part B (Table 2), and Part C (Table 3a inpatients and Table 3b outpatients) in Section 8.1. Clinically significantly abnormal laboratory finding should be followed up until resolution or until the analyte is stable. If the post-treatment data is reported as invalid, an unscheduled visit should be performed to repeat the laboratory safety tests within 2 weeks after Dose 10.

Haematology

Haemoglobin, haematocrit, white blood cell count (total and differential), red blood cell count, platelet count, mean cell volume (MCV), mean cell haemoglobin (MCH), and MCH concentration (MCHC).

Clinical Chemistry

Creatinine, urea (or blood urea nitrogen), AST, ALT, gamma glutamyltransferase, alkaline phosphatase, lactate dehydrogenase, total bilirubin, albumin, total protein, sodium, potassium, chloride, glucose, and calcium.

Note: for the Screening Visit ONLY, AST and ALT analysis can also be conducted at the local laboratory, although a blood sample must also be sent to the Central laboratory for analysis.

Urinalysis

pH, glucose, ketones, blood, protein, and microscopy.

10.1.3.5 Clinical Laboratory Evaluation

The haematology and clinical chemistry safety laboratory analyses will be performed at the following laboratory:

Eurofins Central Laboratory Lancaster
[name]
[name]
USA
[contact]
[contact]

For those analyses that are subcontracted to other laboratories (plasma PK and nasopharyngeal swab samples), the test results will be reported directly to Syneos Health.

Reference ranges will be supplied by Eurofins and used by the Investigator to assess the safety laboratory data for clinical significance and pathological changes.

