7.2 PART C: Objectives and Endpoints

Primary Objectives for Part C	Primary Endpoint

 • Evaluate the antiviral effects of RV521, compared to placebo, on nasopharyngeal shedding of RSV in infants hospitalised with RSV LRTI 	
 • Time-weighted average change from Baseline to Day 7 in RSV viral load measured in nasopharyngeal swabs by RT-qPCR.
Secondary Objectives for Part C	Secondary Endpoints

 • To evaluate virologic parameters derived from the RSV viral load as measured in nasopharyngeal swabs • CCI [REDACTED] 	
 • Virologic parameters derived from the RSV viral load as measured in nasal swabs include but are not limited to: 
 ○ Change from baseline in viral load (RT-qPCR and CBIA) at each time point ○ Time to below viral load quantification limit (RT-qPCR and CBIA) ○ Proportion of subjects with viral load below quantification limit (RT-qPCR and CBIA) at each timepoint throughout the study • CCI [REDACTED]

 To evaluate the clinical efficacy of multiple oral doses of RV521 in infants hospitalised with RSV LRTI Evaluate the safety and tolerability of RV521 given as a multiple dose regimen 	
 Time to resolution in RSV-related symptoms Time to improvement of RSV-related symptoms Reduction in severity of symptoms by RV521, compared to placebo, measured by a composite score over time Use of supplementary oxygen, including, but not limited to, duration and maximum level of O₂ provided Time to normalisation of respiratory rate Safety of RV521 compared to placebo assessed by incidences of AEs, discontinuations due to AEs, SAEs, and clinically significant changes in laboratory tests

Exploratory Endpoints (Part C)
	
 [REDACTED] [REDACTED] [REDACTED]

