##### Secondary Endpoints for Part C

- Safety of RV521 compared to placebo assessed by incidences of AEs, discontinuations due to AEs, SAEs, and clinically significant changes in laboratory tests
- Comparison between RV521 and placebo for changes in viral load over time as for Part B
- CCI [REDACTED]

This document is confidential.

- CCI [REDACTED]

This document is confidential.

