#### **12.4. Laboratory Evaluations**

Laboratory results will be presented for haematology, chemistry and urinalysis.

This document is confidential.

All laboratory results will be converted to Standard International units. Results below or above the normal range will be indicated in the listings.

In the presence of re-tests, original results will be used in the summary tables, however all re-test results will be included in the listings.

For each of Parts A, B and C, continuous laboratory results will be summarised at baseline and at each scheduled post-baseline time point. Summary statistics will be provided for the observed values at each time point, and the corresponding change from baseline. Categorical laboratory results for urinalysis will be summarised at baseline and at each scheduled post-baseline time point. The number and percentage of subjects with laboratory measurements outside of the normal reference range will also be summarised at baseline and at each scheduled post-baseline time point.

Laboratory results will be graded according to NCI CTCAE v5.0, for applicable parameters (haemoglobin, white blood cells, platelets, creatinine, AST, ALT, alkaline phosphatase, lactate dehydrogenase, total bilirubin). The severity will be graded as follows:

- Grade 1: Mild
- Grade 2: Moderate
- Grade 3: Severe
- Grade 4: Life-threatening

For each applicable parameter, the number and percentage of subjects experiencing each abnormality at any time after first dose will be summarised by severity grade and by maximum severity grade.

Shift tables of laboratory results from baseline to maximum post-dose severity grade, including unscheduled visits, will be presented.

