#### **12.6. ECG**

ECG parameters include ventricular heart rate, PR interval, QRS interval, QT interval and QTcB interval.

For each of Parts A, B and C, ECG parameters will be summarised at baseline and at each post-baseline time point. Summary statistics will be provided for the observed values at each time point, and the corresponding change from baseline.

In addition, the investigator's interpretation of the ECGs are also captured. These data will be summarised at baseline and at each post-baseline time point.

Only results from the central ECG machine will be used in the summary tables.

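### Clinically significant laboratory changes are a named Part C safety endpoint, but the SAP has no by-arm summary of them, and nine of 15 chemistry analytes are counted only as in or out of range at scheduled visits

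*Protocol*

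**What the plan says.** Protocol 7.2 lists among the Part C secondary endpoints: "Safety of RV521 compared to placebo assessed by incidences of AEs, discontinuations due to AEs, SAEs, and clinically significant changes in laboratory tests". SAP 4.4 carries the same component under its Part C secondary endpoints: "discontinuations due to AEs, SAEs, and clinically significant changes in laboratory tests". Protocol 10.1.3.5 says how the judgement is to be made: central-laboratory reference ranges are "used by the Investigator to assess the safety laboratory data for clinical significance and pathological changes".

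Protocol 10.1.3.4 lists the clinical chemistry panel, which ends with "albumin, total protein, sodium, potassium, chloride, glucose, and calcium".

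SAP 12.4 plans four kinds of laboratory output:
- summaries of values and changes by visit;
- range counts: "The number and percentage of subjects with laboratory measurements outside of the normal reference range will also be summarised", at baseline and at scheduled visits;
- CTCAE v5.0 grade and maximum-grade tables for nine named parameters;
- shift tables from baseline to the worst post-dose grade, which take in unscheduled visits.

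SAP 6.1 sets the general rule that unscheduled assessments are listed and not summarised. For ECGs, SAP 12.6 says that the investigator's "interpretation of the ECGs are also captured" and that these data will be tabulated. SAP 12.5 does the same for vital signs.

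**The concern.** A safety endpoint named in both documents should lead to an output that states its incidence in each arm. Here the chain stops at the endpoint list. SAP 12.4 neither defines a clinically significant laboratory change nor tabulates one. If the SAP were followed as written, the Part C report would cover AEs, discontinuations and SAEs but not the fourth named component.

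The omission looks like an oversight. The investigator's reading is tabulated for vital signs and ECGs, where it is not a named endpoint, and not for laboratory data, where it is. The legible entries in SAP section 14 do not declare the omission as a change from the protocol.

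It matters most for the ungraded analytes. Protocol 6.6 calls vomiting and diarrhoea expected toxicities of RV521. It is ordinary clinical reasoning, not a statement in the documents, that electrolytes are among the first results a reader would check for consequences of those events.

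**Working it through.** No sample size, power or alpha figure is involved, and the plan states no figure to reproduce. The check is a comparison of lists.

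**1. Is the endpoint reported?** The SAP index of tables has these Part C laboratory tables:

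| Panel | Part C tables | Content | Reports clinical significance |
|---|---|---|---|
| Haematology | 5 (14.3.4.1.1.3.1 to .5) | summary and change; abnormal by visit; by severity; by maximum severity; shift | 0 |
| Chemistry | 5 (14.3.4.1.2.3.1 to .5) | the same five | 0 |
| Urinalysis | 3 (14.3.4.1.3.3.1 to .3) | continuous; categorical; abnormal by visit | 0 |

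Total: 5 + 5 + 3 = 13 tables, none reporting clinical significance. Each panel also has an abnormal-results listing. SAP 12.4 says the listings will mark results above or below range; it mentions no mark for clinical significance. By contrast, the index has Part C tables of the investigator's interpretation for vital signs (14.3.4.2.3.2) and ECG (14.3.4.3.3.1).

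**2. Which chemistry analytes are graded?** Collected under Protocol 10.1.3.4: 15.
- Graded in SAP 12.4: creatinine, AST, ALT, alkaline phosphatase, lactate dehydrogenase, total bilirubin = 6.
- Not graded: urea, gamma glutamyltransferase, albumin, total protein, sodium, potassium, chloride, glucose, calcium = 15 − 6 = 9, and 9/15 = 60%.
- Electrolytes graded: 0 of 4 (sodium, potassium, chloride, calcium).
- The other three graded parameters are haematological (haemoglobin, white cells, platelets), so 6 + 3 = 9 graded parameters in all.

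**3. What happens to an abnormal result?**

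| | Graded parameter | Ungraded chemistry analyte |
|---|---|---|
| Scheduled visit | range count, grade, maximum grade, shift; minimum and maximum | range count; minimum and maximum |
| Unscheduled test | grade count (any time post-dose) and shift table (SAP 12.4) | listing only (SAP 6.1) |
| Severity separated in a laboratory table | yes | no |

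**4. How much does the unscheduled rule matter?** Protocol Tables 3a and 3b schedule safety bloods in Part C at Screening and once afterwards, at Visit Day 7 (40 to 48 hours after Dose 10), with a window of two days either way. A disturbance during the five dosing days that was found by an extra test and had resolved by Visit Day 7 would, for an ungraded analyte, enter no laboratory summary table.

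**The case against.** The strongest reply is that serious values are not lost, and much of it stands.

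- For the nine graded parameters, the grade, maximum-grade and shift tables do separate severe from mild.
- For the other analytes, an extreme scheduled value shows in the minimum or maximum and in the abnormal-results listing.
- Protocol 10.1.3.1 counts an abnormal laboratory finding as a possible AE, requires all AEs to be documented and graded by CTCAE, and SAP 12.3 tabulates TEAEs by severity. Protocol 8.4.5 includes laboratory abnormalities in a Part C pausing criterion.
- Hydration status is assessed repeatedly during dosing and tabulated by severity (SAP 8.6), so vomiting and diarrhoea are not watched through electrolytes alone.

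A reader might therefore infer from the missing table that a serious laboratory value is in general counted like a trivial one. The documents do not support that. It describes only the out-of-range count, and only for ungraded analytes.

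A reader might also infer that the investigator's laboratory judgement already sits in the database. Protocol 10.1.3.5 requires the judgement, but no section says the CRF records it. SAP 12.5 and 12.6 say so only for vital signs and ECG.

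Two further limits apply. The documents do not say which of the nine ungraded analytes CTCAE v5.0 grades, so nine is the most by which the grading list could fall short in chemistry. And outputs for the safety committee are set in a charter that is not among the documents.

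None of this supplies the endpoint. Minima, maxima and listings are not incidences by arm. The endpoint names AEs and laboratory changes separately, and Protocol 10.1.3.4 requires significant findings to be followed up without saying that each must be filed as an AE.

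**Conclusion.** The point holds in a limited form. Part C names clinically significant laboratory changes as a secondary safety endpoint, and the SAP gives it no definition and no by-arm summary: 0 of 13 Part C laboratory tables. For nine of 15 chemistry analytes (60%), including all four electrolytes, the only abnormality count is in or out of range at scheduled visits, and unscheduled results are only listed.

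This rests on two readings. First, SAP 12.4 and the index of tables, as far as they are legible, are the full set of planned laboratory outputs. Second, the unscheduled rule in SAP 6.1 applies wherever SAP 12.4 does not override it, as it does for graded parameters. The documents give no basis for estimating how many infants would be affected, so no such figure is offered.

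The gap does not touch the primary analysis and is cheap to close. SAP version 2.0 still describes Part C as a 1:1 comparison in about 120 subjects, whereas the protocol has three arms and 111, so its Part C content needs amending in any case.

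**What to change.** Protocol 11.1 allows SAP amendments for Part C until database lock and unblinding. In that amendment:

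1. Define the endpoint and add a Safety Population table by arm: number (%) of infants with at least one post-baseline laboratory abnormality judged clinically significant, overall and by analyte, with unscheduled results included. Because the endpoint is worded as changes, state how values already judged significant at baseline are handled.
2. Confirm that the CRF captures the investigator's laboratory judgement. If it does not, define the endpoint from CTCAE grade shifts.
3. Extend the grade, maximum-grade and shift tables to every analyte measured under Protocol 10.1.3.4 that CTCAE v5.0 grades.

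The cost is SAP wording and a few more tables. If the judgement is not on the CRF, collecting it would be a further cost; the grade-shift definition avoids that. Clinical significance is a judgement and may vary between investigators, so the range counts and grades should stay alongside it.
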